Pain sensitization in patients with symptomatic atrial fibrillation compared with asymptomatic patients

[name], PhD¹, [name], BSc¹ [name], PhD¹, [name] BSc PhD², [name], MSci, PhD, DMSci²

1. Department of Cardiology, Faculty of Medicine and Health, Örebro University, Sweden.
2. SMI, Faculty of Medicine, Aalborg University, Aalborg, Denmark.

Correspondence:

[name], PhD

[name], PhD

Department of Cardiology

Department of Cardiology

Örebro University Hospital

Örebro University Hospital

[name]

[name]

[contact]

[contact]

[contact]

[contact]

Email: [contact]

Email: [contact]

Abstract

Background

Atrial fibrillation (AF) is the most common sustained arrhythmia and the number of patients with AF is expected to increase substantially in the coming decades. One third of patients with AF report no AF-associated symptoms, but up to one fourth report severe symptoms such as chest pain. It is well recognized, but unclear why patients' experience of AF-related symptoms, including chest pain, varies so much. Patients with chronic pain show a high degree of central sensitization, i.e. facilitated pain responses to repeated painful stimulation and impaired conditioned pain modulation, compared with controls. It is possible that patients with symptomatic AF may have developed pronounced pain sensitization even in the absence of chest pain as a symptom. No previous study has investigated pain sensitization in patients with AF.

Objective and methods

The primary objective is to assess differences in pain sensitization in patients with symptomatic AF compared with patients with asymptomatic AF. Secondary objectives are to study the association of age, sex, AF duration, comorbidities and health-related quality of life to pain sensitization. A total of 30 patients with permanent AF (15 symptomatic and 15 asymptomatic) will be recruited. Patients will complete an AF-specific symptom score and a generic health-related quality of life questionnaire, and physicians will assess AF-related symptoms. Quantitative sensory testing recordings will be collected by pressure algometry. Assessment of temporal summation of pressure pain and conditioning pain modulation will be used to investigate the involvement of pain sensitization.

Clinical relevance

Date: 2020-11-24

Version: 1.2

This preliminary pilot study will be used to estimate sample size for a larger study in which both patients and control subjects will be recruited, to further investigate whether patients with symptomatic AF have increased pain sensitization compared with patients with asymptomatic AF and controls. The studies may have an impact on individualized management of patients with AF in the future.

Trial registration

The study protocol is registered with ClinicalTrials.gov (NCT...)

Keywords

Atrial fibrillation, Symptoms, Quality of life, Pain, Conditioning pain modulation, Temporal summation

Abbreviations

AF	Atrial fibrillation
AF6	Atrial fibrillation 6 questionnaire
CPM	Conditioned pain modulation
ECG	Electrocardiogram
SF-36	Short form 36 health survey
VAS	Visual analogue scale

Introduction

Background

Atrial fibrillation (AF) is the most common sustained arrhythmia affecting approximately 3% of adults aged 20 years or older in Western countries, and is expected to increase further in the coming decades(1). The presence of AF is independently associated with an increased risk of all-cause mortality and morbidity, largely due to stroke and heart failure, dementia, symptoms, and impaired quality of life(2-7). The management of AF aims to prevent AF-related complications using oral anticoagulation therapy in patients with a high risk of stroke and to reduce symptoms and improve health-related quality of life using a rate (slowing of the ventricular rate) or rhythm control (restoration and maintenance of normal sinus rhythm) strategy(8).

About one third of patients with AF report no AF-associated symptoms, but up to one fourth of patients report severe symptoms such as palpitations, dyspnea, chest discomfort or pain, dizziness and syncope(9-11). In previous studies 9 to 15% of patients with permanent AF reported chest pain as an AF-related symptom(12, 13). In addition, one third of patients with symptomatic AF suffer from psychological distress (anxiety and/or depression), which may also worsen symptoms of AF(11, 14).

It is well recognized, but remains unclear why some patients with AF are asymptomatic whereas others are severely symptomatic. Several studies have evaluated the relationship between patient characteristics and the presence of AF symptoms, and have found that asymptomatic AF is more frequent in men than in women, and in older age(15, 16).

Inconsistent results have been reported for associations between asymptomatic AF and comorbidities(17). Patients with all types of AF can be asymptomatic, but asymptomatic AF

is more common in patients with permanent AF(18). The situation is further complicated by the fact that asymptomatic AF episodes are common even in highly symptomatic patients and that AF interventions such as pulmonary vein isolation increase asymptomatic episodes(19). In conclusion, little is known of the pathophysiological mechanisms underlying AF symptomatology but both somatic and psychological factors are likely involved.

The authors have previously shown that central nervous system responses to visceral and somatosensory nociceptive input are altered in patients who have angina despite normal coronary angiograms compared to healthy volunteers(20). Patients with chronic pain conditions such as osteoarthritis, chronic pancreatitis and irritable bowel syndrome, show a high degree of central sensitization, i.e. facilitated pain responses to repeated painful stimulation and impaired conditioned pain modulation (CPM) compared with controls(21-24). Furthermore, these patients often show a discrepancy between pain intensity and objective measures of disease severity and healthcare personnel often underestimate patients' pain intensity(25, 26). It is also well-known that stress influences pain sensitivity and has been correlated to hyperalgesia in patients with ischemic heart disease(27, 28). It is possible that patients with symptomatic AF have developed pronounced pain sensitization even in the absence of chest pain as a symptom, and in particular facilitated pain responses to repeated painful stimulation, i.e. temporal summation of pressure pain. No previous study has investigated pain sensitization in patients with AF, neither in patients with or without chest pain as a symptom.

Purpose

The primary objective is to assess differences in pain sensitization in patients with symptomatic AF compared with patients with asymptomatic AF.

Hypothesis

We hypothesize that central sensitization is involved in sensing of and discomfort from AF in symptomatic patients, involving neural pathways also involved in perceiving pain. Because of shared pathways, we further hypothesize that patients with AF symptoms have lower pain thresholds than asymptomatic patients with AF.

Clinical relevance

It is well recognized, but unclear why patients' perception of AF varies so much. This preliminary pilot trial will be used to estimate sample size for a larger trial, in which both patients and control subjects will be recruited, to further investigate whether patients with symptomatic AF have increased pain sensitization compared with patients with asymptomatic AF and controls. The studies may have an impact on individualized management of patients with AF in the future.

Material and methods

Study design

Single-center cohort study.

Subject inclusion criteria

Study participants will be recruited from a database of all patients aged 20 years or older with a diagnosis of AF from 1 January 2015 to 31 December 2018 in Örebro County (more than 10 000 patients) extracted from the National Patient Register, that covers all in-patient and outpatient physician visits from both private and public caregivers, and the Medrave 4 patient statistics software that is used in all public general practices in the county. The diagnosis of AF was based on at least one electrocardiogram (ECG) characterized by an absolutely irregular RR interval, no distinct P waves and an atrial cycle length of less than 200 ms. By accepted convention, an episode with these ECG characteristics lasting for at least 30 seconds was diagnostic of AF(8). Permanent AF is defined as persistent AF that is accepted by both the patient and the physician and for which no further attempts to restore or maintain normal sinus rhythm will be undertaken(8).

Further inclusion criteria:

- Male or female subjects \geq 20 years and \leq 75 year, primarily 60 to 70 years old.
- Permanent AF
- Previously completed AF-specific symptoms questionnaire Atrial fibrillation 6 questionnaire (AF6)
- Written informed consent

Subject exclusion criteria

Date: 2020-11-24

Version: 1.2

- Paroxysmal or persistent AF (AF that terminates spontaneously or with intervention, respectively(8))
- Previous pulmonary vein isolation
- Psychiatric or cognitive condition
- Pregnancy
- Previous/current drug or alcohol abuse
- Previous neurological or concomitant musculoskeletal disorders
- Continuous analgesic medication

Examinations

All potential patients will receive written information about the study and will thereafter be contacted by telephone and offered an outpatient visit to a physician at the Department of cardiology, Örebro University Hospital, Örebro, Sweden. After obtaining written informed consent, patients will be asked to complete the AF6 and the Short form 36 health survey (SF-36) questionnaires before a 12-lead ECG is obtained. Patients will also be asked to rate the symptom chest pain on the Visual analogue scale (VAS) (0 to 10) and to draw the pain area on a body chart. Comorbidities, medications and duration of AF will be documented and a routine clinical examination will be performed, and the modified European Heart Rhythm Association symptoms scale assessed. Quantitative sensory testing recordings will be collected by pressure algometry. The patients will be asked not to take any analgesic medication 24 hours before the examination. No follow-up visits are scheduled. Subjects will be divided into two groups based on their previous AF6 symptom scores; asymptomatic patients with an AF6 sum score of 0, and symptomatic patients with an AF6 sum score of ≥30.

Symptom assessment

The patient-reported AF6 questionnaire includes six items (breathing difficulties at rest and upon exertion, limitations in day-to-day life, feeling of discomfort, tiredness and worry/anxiety due to AF) and a score of 0 (no symptoms) to 10 (severe symptoms) is reported for each item, and all scores are added into a single sum score. Sum scores range from 0 to 60, with higher values reflecting more severe AF-related symptoms. The AF6 includes a recall period of the last 7 days(29, 30).

The physician-assessed modified European Heart Rhythm Association symptoms scale is used for symptom severity assessment in patients with AF, relating specifically to the time when patients feel symptoms of AF. Patients in class I are considered to have no symptoms, in class IIa mild, class IIb moderate, class III severe and in class IV disabling symptoms of AF(8, 31).

Health-related quality of life

The patient-reported SF-36 has a recall period of four weeks and consists of 36 items assessing eight domains ranging from 0 to 100, with higher values indicating better health-related quality of life. The eight domains generate two summary measures: the physical component summary and the mental component summary scores, which will be used to assess health-related quality of life(32).

Clinical examination

A cardiovascular examination including blood pressure measurement will be performed. The blood pressure will be measured after 15 minutes of rest by an automatic sphygmomanometer.

Quantitative sensory testing

Pressure pain threshold

The pressure pain thresholds (PPTs) is defined as the minimal amount of pressure where a sense of pressure first changes to pain. Participants will be instructed to press the 'stop' button of the algometer as soon as the pressure results in the first sensation of pain.

Pressure will be increased at a rate of approximately 30 kPa/s. The 1-cm² probe of the handheld pressure algometer (Somedic AB, Sweden) will be placed perpendicularly to the skin. PPTs will be assessed over the sternum at the level of intercostal spaces 3–5 and over the tibia bone(27). The PPTs will be measured three times on each site, and the mean of the three measurements will be used for statistical analysis. Low PPTs indicate sensitization.

Temporal summation of pressure pain

A Pin prick (tip area, 0.2mm²) with a weighted load (Aalborg University, Denmark) will be used to induce temporal summation of pressure pain (TSP) as previously conducted in other pain studies(33-35). A force of 50 g will be applied once over the sternum at the level of intercostal spaces 3–5 and over the tibia bone and the patient will be asked to rate the pain intensity on the VAS (0 to 10). Then 10 consecutive stimuli will be applied (1 s interval between consecutive stimuli) to the same site and the subject will be asked to rate the pain intensity of the last stimulation on the VAS. TSP will be calculated as the difference in the

pain intensity between the first and the last stimulation. High TSP scores indicate facilitated temporal summation.

Conditioning pain modulation

The right hand up to the wrist will be immersed into stirred cold water (2–4 °C, measured in the water) for 2 min (the so called cold pressor test). Before the immersion the PPTs will be assessed from the sternum and the tibial bone, at the end of the two min immersion the PPTs will be assessed again and this will be repeated again 10 min after the hand is withdrawn from the water. The conditioning pain modulation index will be assessed as the increase in PPTs during the immersion as compared to the pre-immersion PPTs. The lower the difference is the more sensitization.

Primary endpoint

The primary objective is to assess differences in pain sensitization in patients with symptomatic AF compared with patients with asymptomatic AF.

Secondary endpoint

Secondary objectives are to study the association of age, sex, AF duration and comorbidities and physical and mental component summary scores to pain sensitization.

Ethics approval

The study protocol is approved by the Swedish Ethical Review Authority (2020-01619).

Statistics and data management

Date: 2020-11-24

Version: 1.2

Data collected during the study will be coded.

Statistical analysis

Data will be presented as mean and standard deviation. A one-way ANOVA will be used for demographic parameters and to compare the groups. Pearson correlations will be used for linear estimates and Spearman's correlations for non-linear parameters. All analyses will be adjusted for age. Analyses will be performed using IBM SPSS Statistics 22 (Armonk, NY, USA) or STATA release 14 (College Station, TX, USA).

Sample size calculations

As no previous trial of pain sensitization in patients with AF has been performed, a pilot trial is necessary to calculate sample size for a larger study.

Database and Case report form

A case report form will be filled out and coded for each patient. The investigators are responsible for ensuring the accuracy, completeness, legibility and timeliness of the data recorded in the case report forms.

Documentation and data collection

Criteria for inclusion, informed consent, the decision to include the subject and the subject number will be documented in the subject's hospital record.

Insurance

The subjects in the study are covered by the Swedish patient insurances.

Economy

The trial is an academic study conceived and conducted by healthcare personnel. The study is independent of commercial interests. Study logistics, handling of data and statistical

assessment will be financed by the Department of Cardiology, Örebro University Hospital, Sweden. The investigators will apply for grants from public funds.

Ethical considerations

The study will be conducted in accordance with the Declaration of Helsinki. The cold pressor test activates the sympathetic nervous system and increases blood pressure and heart rate, and there is a slight risk of angina during the test. There are otherwise no known risks or complications associated with the quantitative sensory testing but it may cause some temporary mild to moderate discomfort.

The patient is free to stop the testing at any time, and in case of angina the testing will be stopped and the patient will be closely monitored and administered sublingual nitroglycerin.

Risks, side effects, advantages and disadvantages in participation

Subjects will be treated according to standard clinical practice. There is a slight risk of the test causing angina chest pain. However, we do not expect that subjects will have any disadvantages from participating in the study. The risk of complications during quantitative sensory testing is considered low.

Guidelines for obtaining informed consent

Subjects will enter the study after signing the informed consent form. Candidate participants will receive written information of the study, and oral information by a physician participating in the study. The subjects will be given time to think through participation in the study and to ask questions. Informed consent will be obtained by a Good Clinical Practice qualified physician participating in the study.

Withdrawal

Date: 2020-11-24
Version: 1.2

A subject can withdraw from the study at any time. Data collected up to the end of follow-up will be used in the final analysis of the study.

Publication

Results, positive as well as negative or inconclusive, will be published in an international medical journal, primarily in a cardiology journal.

End of trial and archiving

The study will end when the last subject has signed informed consent, completed the questionnaires and has undergone clinical examination and quantitative sensory testing. The steering committee reserves the right to terminate the study prematurely e.g. if the study participant recruitment is too slow, if study participant retention in the study is insufficient or if undue risk related to the quantitative sensory testing arises. Data collected during the study will be archived for at least 10 years after the study has been completed.

References

1. Zoni-Berisso M, Lercari F, Carazza T, Domenicucci S. Epidemiology of atrial fibrillation: European perspective. (1179-1349 (Print)).
2. Bjorck S, Palaszewski B Fau - Friberg L, Friberg L Fau - Bergfeldt L, Bergfeldt L. Atrial fibrillation, stroke risk, and warfarin therapy revisited: a population-based study. (1524-4628 (Electronic)).

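### The age association is to be summarised by a correlation coefficient in a sample selected on age, so its size will depend on the recruitment mix; a slope with a 95% CI and an influence check would serve better

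*Combined protocol and SAP*

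**What the plan says.** Under Further inclusion criteria, patients from 20 to 75 years are eligible, "primarily 60 to 70 years old". The protocol does not say how many may fall outside that band, nor why it was chosen. The Abstract sets the size: "A total of 30 patients with permanent AF (15 symptomatic and 15 asymptomatic) will be recruited".

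Under Secondary endpoint, age is the first variable listed: "Secondary objectives are to study the association of age, sex, AF duration and comorbidities and physical and mental component summary scores to pain sensitization".

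Under Statistical analysis, the rule for associations is general: "Pearson correlations will be used for linear estimates and Spearman's correlations for non-linear parameters". It does not say which coefficient applies to age. Pearson is the natural default for two continuous variables if the relation is taken as linear. No slope, confidence interval or influence check is mentioned. The same section states "All analyses will be adjusted for age", which cannot apply to the age association itself, and no exception is made for it.

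Under Sample size calculations, N = 30 is justified only by the statement that "a pilot trial is necessary to calculate sample size for a larger study".

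**The concern.** The plan names age as an association to study, concentrates recruitment so as to remove much of the age variation, and then summarises the result with a statistic whose size depends on that variation. Two things follow, in opposite circumstances. If almost everyone is in the band, r is pulled towards zero relative to its value over a wider age range. If one or two patients lie well outside it, they supply a large part of the age variation and weigh heavily on r.

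In either case the reported r would partly describe how loosely the recruiters applied a preference. The Publication section commits to publishing negative and inconclusive results, and the pilot is to inform a larger study. A small r could be taken to mean that age is unimportant there.

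**Working it through.** The plan gives no figure to reproduce: there is no alpha, power, effect size or target precision.

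**Inputs from the protocol.** n = 30; eligible ages 20–75; preferred band 60–70.

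**Assumptions not in the protocol.** Two-sided alpha 0.05; ages uniform over the band; wider age SD S of 6, 8 or 10 years; a correlation of 0.30 over the wider range; a linear relation with constant residual variance.

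**1. Attenuation.** Uniform ages over 60–70 have SD 10/√12 = 2.89 years. With u = 2.89/S, the expected correlation in the band is r′ = r·u / √(1 − r² + r²u²). Power uses Fisher's z: atanh(r)·√27 against 1.96, both tails.

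| Wider age SD | u | r′ for r = 0.30 | Power, n = 30 |
|---|---|---|---|
| no band | 1 | 0.30 | 36% |
| 6 | 0.48 | 0.15 | 12% |
| 8 | 0.36 | 0.11 | 9% |
| 10 | 0.29 | 0.09 | 8% |

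For scale, |r| must exceed 0.361 to be significant at n = 30, 80% power needs r of about 0.49, and the 95% CI around an observed r of 0.10 is −0.27 to 0.44.

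**2. The slope under the same restriction** (S = 8, outcome in SD units of the wider population). Without the band, the slope is 0.30/8 × 10 = 0.375 per 10 years. In the band, the outcome SD is √(0.91 + 0.09 × 0.36²) = 0.96, and the slope is 0.113 × 0.96/2.89 × 10 = 0.375. The slope is unchanged while r falls from 0.30 to 0.11.

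Precision does suffer. The residual SD is √0.91 = 0.954. The standard error per 10 years is 10 × 0.954/(8 × √29) = 0.22 without the band and 10 × 0.954/(2.89 × √29) = 0.61 with it. Multiplying by t = 2.05 gives half-widths of about 0.45 and 1.26. In the band, an estimate of 0.375 would carry an interval of about −0.88 to 1.63, which shows plainly how little is known.

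**3. Influence.** Take 29 ages evenly spaced over 60–70 (mean 65, sum of squares 258.9) and add one patient aged a. The total sum of squares is 258.9 + (29/30)(a − 65)². That patient's share is [(29/30)(a − 65)]² divided by the total, and leverage is 1/30 plus the share.

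| Age | Total | Own part | Share | Leverage |
|---|---|---|---|---|
| 55 or 75 | 355.6 | 93.4 | 26% | 0.30 |
| 50 | 476.4 | 210.3 | 44% | 0.47 |
| 45 | 645.6 | 373.8 | 58% | 0.61 |

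A single patient aged 50 also raises the age SD from 3.04 (the 29 alone) to √(476.4/29) = 4.05. With S = 8, the expected r then moves from 0.12 to 0.16 with no change in the underlying relation.

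**4. What influence does to the result.** In simulations with no true association, type I error stayed near 5% whether the outside ages were 75, 45 or 30. When the one outside patient also scored +2 SD, Pearson was nominally significant in 14% of runs at age 75 and 20% at age 50; Spearman in about 6% of runs at either age. Among significant Pearson results, dropping the outside patient removed significance in 51% (age 75) or 74% (age 45).

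**The case against.** Several counter-arguments stand.

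- *A reader might infer that the plan prescribes Pearson for age.* It does not. Spearman is equally available under its wording, and it removes most of the leverage, though not the range restriction. Pearson is only the default if linearity is assumed.
- *A reader might infer that the sample will be severely restricted, or that one patient will decide the result.* The documents support neither. The preference has no quota, so the degree of restriction is unknown. The two problems also pull against each other, and with many patients spread outside the band both fade. A patient aged 71–75 supplies at most about 26% of the age sum of squares under the even-spread assumption. Deciding the result takes a distant age together with an extreme outcome.
- *A slope does not rescue the analysis.* In simple regression its test is the same as the Pearson test, so p-value, power and leverage are identical. Only the dependence of the estimate's size on age selection is removed; influence is addressed by the repeat analysis.
- *Narrowing the age range outright would be no cure.* In the age-45 example, replacing that patient with one in the band cuts the age sum of squares from about 646 to 267 and raises the slope's standard error by √(646/267) = 1.56.
- *It is one secondary association in a pilot.* Even without restriction, power at r = 0.30 is 36%, so a null would be uninformative anyway.

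What remains is that the plan commits to a summary whose size depends on the recruitment mix, and provides neither an interval nor an influence check.

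**Conclusion.** The point holds as a minor one about reporting a named secondary objective. If nearly all patients are aged 60–70, a correlation of 0.30 would be expected to appear as about 0.09–0.15. That rests on an assumed wider age SD of 6–10 years and on uniform ages in the band. One patient aged 50 among 29 in the band would carry 44% of the age variation, and one aged 55 or 75 would carry 26%. These are illustrations, because the protocol gives no age distribution.

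A regression slope is not shifted by selection on age, provided the relation is linear, and its interval shows the imprecision. A reader might take this as a flaw in the main comparison of symptomatic with asymptomatic patients. It is not: that comparison is unaffected, and concentrating ages plausibly limits age confounding there.

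**What to change.** In Statistical analysis, add wording to this effect:

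- The association of age with each pain sensitization measure is estimated as a regression slope per 10 years with its 95% CI, and this is the main estimate. If a correlation is also given, name the coefficient.
- The slope is re-estimated without patients outside 60–70, or a rank correlation is reported alongside, as an influence check.
- The result is interpreted only for the ages actually sampled, and a null estimate is not read as absence of association.
- The general age adjustment does not apply to this analysis.

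The cost is a few lines of text and one repeat analysis. Recruitment, sample size and data collection are unchanged. Power is not improved; the gain is an estimate that does not depend on the recruitment mix (given linearity), a visible interval, and a check on whether one or two patients drive it.

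### No masking of the sensory tester and no standard instruction script are specified, so expectation can bias the group difference that is meant to size the larger study

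*Combined protocol and SAP*

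**What the plan says.** The Examinations section describes one outpatient visit with no follow-up. It lists, in this order:

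- AF6 and SF-36, then a 12-lead ECG;
- a chest-pain rating and pain drawing ("Patients will also be asked to rate the symptom chest pain on the Visual analogue scale (VAS) (0 to 10"));
- comorbidities, medication and a clinical examination, "and the modified European Heart Rhythm Association symptoms scale assessed";
- "Quantitative sensory testing recordings will be collected by pressure algometry".

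The same section assigns patients to groups by their previous AF6 sum score, 0 or at least 30, so group is settled before the visit.

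The Quantitative sensory testing section describes three measures at the sternum and tibia. The pressure pain threshold (PPT) uses a handheld algometer: "Pressure will be increased at a rate of approximately 30 kPa/s". Temporal summation (TSP) uses a weighted pin prick and pain ratings that the patient is asked for. Conditioned pain modulation (CPM) is the change in PPT during cold-water immersion.

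The Hypothesis section expects that "patients with AF symptoms have lower pain thresholds than asymptomatic patients with AF". The Abstract says of the result: "This preliminary pilot study will be used to estimate sample size for a larger study".

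The documents do not mention blinding, masking, an independent tester or scripted instructions. The statement under Statistics and data management that data are coded concerns data handling; it does not conceal group from the tester.

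**The concern.** Three features combine. The outcomes are subjective responses elicited by an operator. The team has stated which group should be more sensitive. The groups are extremes of a symptom score, so a tester who has read the questionnaires or assigned the symptom class could largely infer group. A tester who expects lower thresholds or more summation in a symptomatic patient can influence the result through the wording of instructions, encouragement, or the way a rating is requested.

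The damage does not depend on a significance test in the pilot. The pilot estimate is to be carried into the sample size of a larger study, so an inflated difference would make that study too small. The planned age adjustment cannot remove the bias, and once testing has been done unmasked no later analysis can separate it from sensitization.

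**Working it through.** **What is explicit and what is inferred**

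| Point | Status in the documents |
|---|---|
| Group known before the visit (previous AF6) | Explicit, Examinations |
| Questionnaires before ECG | Explicit, Examinations |
| Sensory testing after chest-pain rating, body chart and symptom grading | Inferred from the order of the text |
| Who does the testing and what that person knows | Not stated |
| Instruction script | Not stated; the only instruction described is when to press stop |
| Expected direction | Explicit for thresholds, Hypothesis |

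**The plan's own figure.** The Abstract says: "A total of 30 patients with permanent AF (15 symptomatic and 15 asymptomatic) will be recruited". No effect size, SD, alpha or power lies behind the 30; Sample size calculations says only that "a pilot trial is necessary to calculate sample size for a larger study". There is nothing to reproduce, and the point does not depend on it.

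**Illustration 1: false positives in the pilot.** Assumptions: two-sided 5% test, 15 per group, no age adjustment, no true difference, artefactual shift b in SD units. A two-group one-way ANOVA is equivalent to a t-test on 15 + 15 − 2 = 28 degrees of freedom, with critical value 2.048. The noncentrality is b × √(15/2) = 2.739b.

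| Assumed shift b | Noncentrality | Chance of a significant result |
|---|---|---|
| 0 | 0 | 5.0% |
| 0.2 SD | 0.548 | 8.3% |
| 0.3 SD | 0.822 | 12.5% |
| 0.5 SD | 1.369 | 26.2% |

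**Illustration 2: the larger study.** Assumptions: true difference 0.5 SD, bias 0.3 SD, 80% power, two-sided 5%, normal approximation. Then n per group = 2 × (1.960 + 0.842)² / d² = 15.70 / d².

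- Sized on the true difference: 15.70 / 0.25 = 62.8, so 63 per group.
- Sized on the inflated 0.8 SD: 15.70 / 0.64 = 24.5, so 25 per group.
- Real power at 25 per group: Φ(0.5 × √(25/2) − 1.960) = Φ(−0.192), about 42%.

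The bias sizes are assumed in both illustrations. The documents give neither an SD nor any estimate of tester effect.

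**The case against.** The Quantitative sensory testing section contains real safeguards. The patient, not the operator, presses stop. Each PPT is a mean of three measurements. The pin-prick load is fixed at 50 g with a 1-second interval. TSP and CPM are within-patient differences, so a constant shift in a patient's readings cancels. All of this stands and narrows the room for bias. It does not control how instructions are given, whether patients are prompted, or how ratings are elicited. Nor does it cancel an influence that differs between the first and last stimulus, or between baseline and immersion.

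A reader might go further than the documents allow in several ways:

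- *That the tester knows the group, making this an open-label comparison.* The protocol is silent. It permits an unmasked tester but does not state one.
- *That the order of testing is fixed as listed.* The paragraph is not strictly chronological: after the sensory testing it goes on to the analgesic restriction for the preceding 24 hours and to grouping by an earlier score.
- *That group would be obvious on the day.* Grouping uses a previous AF6 with a 7-day recall, and no interval to the visit is given.
- *That the approximate pressure ramp lets the operator set the threshold.* The patient stops the ramp, and the documents give no tolerance, reaction time or SD from which to derive an effect. Nothing here rests on it.
- *That filling in symptom scores primes the symptomatic group more.* All patients complete the same instruments, so a differential effect is plausible but assumed.

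It is also fair to say that this is a 30-patient pilot and that patients cannot be masked to their own symptoms. Masking the tester therefore removes only part of the bias.

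**Conclusion.** The concern holds as a gap in specified safeguards: there is no masking of the sensory tester and no standard script, in a comparison of elicited responses between extreme groups with a stated expected direction. Expectation can create or exaggerate the difference. The documents do not show that it will, or by how much.

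The false-positive rates of 8%, 12.5% and 26%, and the fall in the larger study's power to about 42%, show what assumed biases would do under an assumed two-sided 5% test without age adjustment. They are not estimates for this study. The change should be made before testing starts, because the plan's purpose is to pass this estimate on to a larger study.

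**What to change.** Add to Examinations:

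1. The person doing the sensory testing, chosen from existing study staff, is not told the previous AF6 score or group, and does not see the visit questionnaires, body chart or physician symptom class until the tests are recorded.
2. A fixed instruction script is used for PPT, TSP and CPM.
3. Patients are asked not to discuss their AF symptoms during testing. This leaves untouched their freedom to stop and the protocol's provisions for angina during the test.
4. The tester records a guess of group after the tests, so that masking can be checked.
5. If one physician does both jobs, the symptom grading and review of the questionnaires follow the sensory testing. The patient can still complete the chest-pain rating and body chart beforehand, unseen by the tester. Moving that rating to after the tests would place it after painful stimulation of the sternum and a cold pressor test.

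The cost is a few lines of procedure, with no change to sample size, endpoints or clinical management. Staffing is not described, so a separate tester is an assumption; item 5 covers the case where there is none. Masking will be imperfect because patients may reveal their symptoms, and any priming from self-completed questionnaires remains.
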